#### 6.12.4.3. Injection Site Reaction

The injection site reactions will be searched by MedDRA PTs from all TEAEs. The number and percentage of patients experiencing treatment-emergent injection site reaction will be summarized and compared by treatment group using Fisher's exact test.

For injection site reactions identified by MedDRA PTs, the presence and severity of erythema, induration, pain, pruritus and edema (collected on the eCRF) will be summarized for each treatment. There will be no statistical comparison between treatments.

#### 6.12.4.4. Hepatobiliary Events

##### 6.12.4.4.1. *Treatment-Emergent Potential Hepatic Disorder*

The percentages of patients with treatment-emergent drug-related hepatic disorder events will be summarized and compared by treatment group using MedDRA PT nested within each SMQ ordered by decreasing frequency. The following SMQs based on MedDRA will be used to identify potential hepatic disorders:

- broad and narrow terms in the Liver related investigations, signs and symptoms SMQ (20000008)
- broad and narrow terms in the Cholestasis and jaundice of hepatic origin SMQ (20000009)
- broad and narrow terms in the Hepatitis non-infections SMQ (20000010)
- broad and narrow terms in the Hepatic failure, fibrosis and cirrhosis and other liver damage SMQ (20000013)
- narrow terms in the Liver-related coagulation and bleeding disturbances SMQ (20000015)

The percentage of patients with any 1 of the terms will be summarized in addition to the percentages for each MedDRA PT. The percentages of patients with potentially drug-related hepatic disorders that led to permanent study treatment discontinuation will be summarized similarly.

##### 6.12.4.4.2. *Liver Enzyme Lab Values*

The liver enzyme measures (alanine aminotransferase [ALT], aspartate aminotransferase [AST], alkaline phosphatase [ALP], direct bilirubin, total bilirubin) will be summarized by treatment group. Post-baseline value and the change from baseline (last nonmissing value before randomization) to post-baseline value at Week 26 visit (planned test) will be summarized for patients who have both a baseline and at least 1 postbaseline result, and compared between treatment groups by using ANCOVA model with the term of treatment and baseline value of the response variable. All analyses will be provided in SI units.

The last nonmissing observation at or prior to Week 26 (including early discontinuation visits) will also be analyzed by an ANCOVA model with the term of treatment, baseline value of response variable.

##### 6.12.4.4.3. *Treatment-Emergent Elevation of Liver Enzyme Lab Values*

The percentages of patients with the following elevations in hepatic laboratory tests at any time during the treatment period (0 to 26 weeks) will be summarized between treatment groups:

- The percentages of patients with post-baseline ALT measurement  $\geq 3$  times (3X), 5 times (5X), and 10 times (10X) the Covance upper limit of normal (ULN) will be summarized for all patients with a post-baseline value by the following baseline categories:  $\leq 1X$ ,  $>1X$  to  $<3X$ ,  $\geq 3X$ , missing.

- The percentages of patients with post-baseline AST measurement greater than or equal to 3X, 5X, and 10X the Covance ULN will be summarized for all patients with a post-baseline value by the following baseline categories:  $\leq 1X$ ,  $>1X$  to  $<3X$ ,  $\geq 3X$ , missing.
- The percentages of patients with post-baseline total bilirubin measurement  $\geq 2$  times (2X) the Covance ULN will be summarized for all patients with a post-baseline value by the following baseline categories:  $\leq 1X$ ,  $>1X$  to  $<2X$ ,  $\geq 2X$ , missing.

Baseline will be the maximum observation in the baseline period including the lead-in period. The maximum value will be the maximum value from the treatment period. Planned and unplanned tests will be included.

Graphical profiles of ALT, AST, total bilirubin, and ALP will be provided for patients with an ALT or AST  $\geq 3X$  ULN or total bilirubin  $\geq 2X$  ULN during the treatment period. A listing for these patients will also be provided, including the actual measurement of ALT, AST, ALP, and total bilirubin, the corresponding reference high limits, demographics, disposition, drug exposure and AEs. The review for these patients includes an assessment of the proximity of any ALT or AST elevation to any total bilirubin elevation, ALP levels, other potential causes, and the temporal association with events such as nausea, vomiting, anorexia, abdominal pain, or fatigue.

All patient data, regardless of whether on IP, will be used for the above analyses related to hepatobiliary events.

#### **6.12.5. Clinical Laboratory Evaluation**

The data from safety laboratory measures will be summarized at Week 26 where the lab test is planned to be collected. Postbaseline and change from baseline to postbaseline for laboratory tests will be summarized for patients who have both baseline and at least 1 post-baseline result and compared between treatment groups by using ANCOVA model with the term of treatment and baseline value of the response variable. Analyses will be provided in SI units.

The last nonmissing observation at or prior to Week 26 (planned tests including early termination) will also be analyzed by an ANCOVA model with the term of treatment, baseline value of the response variable.

The percentages of patients with treatment-emergent abnormal, high, or low laboratory results at any time during the treatment period (0 to 26 weeks) will be summarized for patients who have both baseline and at least 1 post-baseline result and compared between treatment groups using Fisher's exact tests. A treatment-emergent abnormal result is defined as a change from normal at all baseline visits to abnormal at any time during the treatment period. A treatment-emergent high result is defined as a change from a value less than or equal to the high limit at all baseline visits to a value greater than the high limit at any time during the treatment period. A treatment-emergent low result is defined as a change from a value greater than or equal to the low limit at all baseline visits to a value less than the low limit at any time during the treatment period.

Planned and unplanned measurements will be included. CCI

be used to define the low and high limits. Only patients who have normal baseline values for the analysis being performed will be included in the analysis for treatment-emergence.

Liver enzymes measures will not be included in the above analyses as different analyses will be used as described in Section 6.12.4.4.2 and Section 6.12.4.4.3.

### 6.12.6. Vital Signs and Other Physical Findings

Post-baseline measurements and change from baseline to post-baseline for vital signs and physical characteristics (systolic blood pressure [SBP], diastolic blood pressure [DBP], pulse rate, weight, BMI) at the scheduled visits will be summarized for patients who have both baseline and at least 1 post-baseline result.

The measurements during the treatment period (0 to 26 weeks) will be analyzed by an MMRM model with treatment, baseline value of the response variable, visit, and visit by treatment interaction as fixed factors and patient as the random factor.

The weight measurement during the lead-in period will also be analyzed by an MMRM model with Visit 2 value of the response variable, randomized treatment, visit and treatment-by-visit interaction as fixed factors, and patient as the random factor. The analysis will be conducted on all randomized patients.

An ANCOVA model will also be used for the analysis of the last nonmissing observation (including early discontinuation visit) during the treatment period and during the entire study (up to Visit 801). The ANCOVA models are the same as those used for clinical laboratory measures.

The percentages of patients with treatment-emergent high or low vital signs and weight at any time during the treatment period (0 to 26 weeks) or during the entire study including safety follow-up period will be summarized by treatment group for patients who have both baseline and at least 1 postbaseline measurement. A treatment-emergent high result is defined as a change from a value less than or equal to the high limit at all baseline visits to a value greater than the high limit at any time that meets the specified change criteria during the treatment period or during the entire study including safety follow-up period. A treatment-emergent low result is defined as a change from a value greater than or equal to the low limit at all baseline visits to a value less than the low limit at any time that meets the specified change criteria during the treatment period or during the entire study including safety follow-up period. Treatment comparison will be based on Fisher's exact test. Table 6.6 will be used to define the low and high limits and change thresholds.

**Table 6.6. Categorical Criteria for Abnormal Treatment-Emergent Blood Pressure and Pulse Measurement, and Categorical Criteria for Weight for Adults**

Parameter	Low	High
Systolic BP (mm Hg) (forearm at heart level)	$\leq 90$ and decrease from baseline $\geq 20$	$\geq 140$ and increase from baseline $\geq 20$
Diastolic BP (mm Hg)	$\leq 60$ and decrease from baseline $\geq 10$	$\geq 90$ and increase from baseline $\geq 10$

(forearm at heart level)		
Pulse (bpm) (Supine or sitting)	<60 and decrease from baseline $\geq 15$	>100 and increase from baseline $\geq 15$
Weight (kg) (Consistent clothing and timing in relationship to meals and voiding)	(Loss) decrease $\geq 7\%$	(Gain) increase $\geq 7\%$

Abbreviations: BP = blood pressure.

[figure not shown]

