Objectives	Endpoints
Other Secondary Objectives (Continued)	

 To compare LY900014 and insulin lispro with respect to the proportion of patients achieving HbA1c targets 	
 The proportion of patients with HbA1c <7% and ≤6.5% at Week 26
Tertiary/Exploratory Objectives	

 To compare the safety of LY900014 relative to insulin lispro 	
 Adverse events, vital signs, chemistry, and hematology laboratory measures

 To compare the incidence of treatment-emergent anti-insulin lispro antibodies for LY900014 and insulin lispro 	
 Incidence of treatment-emergent positive anti-insulin lispro antibodies

 To compare LY900014 and insulin lispro with respect to quality of life as measured by the EQ-5D-5L 	
 Change from baseline in EQ-5D-5L UK-population based health state index score and EQ-VAS score at Week 26

 To compare LY900014 and insulin lispro with respect to diabetes treatment satisfaction as measured by the ITSQ 	
 Change from baseline in ITSQ regimen inconvenience and lifestyle flexibility domain scores at Week 26

 To compare LY900014 and insulin lispro with respect to the impact that diabetes has on the ability to work and perform regular activities as measured by the WPAI-GH 	
 Change from baseline in WPAI-GH item scores at Week 26

 To compare LY900014 and insulin lispro with respect to changes in body weight 	
 Change from baseline to Week 26 in weight (kg)

 To compare LY900014 and insulin lispro with respect to glycemic variability 	
 Within-day and between-day glycemic variability measured by the standard deviation and the coefficient of variation of 10-point SMBG profiles

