Baseline is defined as the last nonmissing measurement at or before the randomization visit (Visit 8) unless otherwise specified.

A restricted maximum likelihood-based, mixed-effect model repeated measure (MMRM) analysis will be used to analyze continuous longitudinal variables. All the longitudinal observations at each scheduled postbaseline visit will be included in the analysis. The model for the analysis of the primary efficacy endpoint of change from baseline in HbA1c will include the fixed class effects of treatment, strata (country, type of basal insulin, and number of prandial doses at entry), visit, and treatment-by-visit interaction, as well as the continuous, fixed covariate of baseline value. For analyses of variables other than HbA1c, the HbA1c stratum ($\leq 8.5\%$, $> 8.5\%$) will be included in the model. An unstructured covariance structure will be used to model the within-patient errors. Significance tests will be based on least squares (LS) means and Type III tests. If this analysis fails to converge, the following covariance structures will be tested in order:

- Toeplitz with heterogeneity
- Autoregressive with heterogeneity
- Compound symmetry with heterogeneous variances
- Toeplitz
- Autoregressive
- Compound symmetry without heterogeneous variances

The first covariance structure that converges will be used. The Kenward-Roger approximation will be used to estimate denominator degrees of freedom.

An analysis of covariance (ANCOVA) will also be used to analyze continuous variables. The model for the change from baseline to the Week 26 HbA1c endpoint will include treatment and strata (country, type of basal insulin, and number of prandial doses at entry) as fixed effects and baseline as a covariate. Unless otherwise stated, missing endpoints will be imputed using the last-observation-carried-forward (LOCF) approach, using only postbaseline data. For analyses of variables other than HbA1c, the HbA1c stratum ($\leq 8.5\%$, $> 8.5\%$) will be included in the model.

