10.3.3.3. Tertiary/Exploratory Analyses

Continuous variables and the change from baseline for these variables will be analyzed either by the MMRM or ANCOVA models described in Section 10.3.1. Categorical variables will be analyzed either by model (for example, logistic regression) or by Fisher's exact test or Pearson's chi-square test. Analysis details for the tertiary endpoints will be described in the SAP.

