Total daily basal insulin dose, total daily prandial insulin dose, total insulin dose, and the ratio of prandial insulin dose to total insulin dose during the lead-in period will be summarized by visit for the Randomized Population. The actual and change from Visit 2 values will be compared between treatment groups using an MMRM model including the corresponding dose at Visit 2, treatment, strata (country, type of basal insulin during the lead-in period, the number of prandial doses at study entry and HbA1c stratum at baseline), visit, treatment-by-visit interaction in the model as fixed factors and patient as a random factor. The actual and change from Visit 2 at Visit 8 (LOCF) will be compared using ANCOVA model including the corresponding dose at Visit 2, treatment, strata (country, type of basal insulin during the lead-in period, the number of prandial doses at study entry and HbA1c stratum at baseline). Doses will be summarized in U and U/kg. Basal insulin dose will be summarized independently for glargine and degludec as well as combined.

Up to 3 OAMs (metformin, dipeptidyl peptidase-4 inhibitor [DPP-4] inhibitor, sodium-glucose co-transporter 2 [SGLT2] inhibitor, sulfonylurea, meglitinide and alpha-glucoside inhibitor) are allowed prior to the study, and up to 2 OAMs (metformin and SGLT2 inhibitor) are allowed during the lead-in and treatment periods. The proportion of patients who were treated with OAMs (by class of OAM) at each visit will be summarized and compared between treatment groups using Fisher's exact test. The number of OAMs per patient will also be summarized by treatment and by period: lead-in period (Visit 2 to Visit 8) and treatment period (Visit 8 to Visit 18).

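### SAP 6.12.6 names no within-patient covariance for the weight and vital-sign MMRM; read literally it is a random-intercept model, which can misstate the Week 26 weight interval and departs from the protocol's model for that objective

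*SAP*

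**What the plan says.** **Protocol.** Section 10.3.1 describes a restricted maximum likelihood MMRM that "will be used to analyze continuous longitudinal variables". For that model, "An unstructured covariance structure will be used to model the within-patient errors". If the fit fails to converge, six simpler structures are tried in order, and the last is "Compound symmetry without heterogeneous variances". The HbA1c model carries country, type of basal insulin and number of prandial doses, and the HbA1c stratum is added for other variables. Change in weight to Week 26 is a tertiary objective (Table ITSE.1). For tertiary endpoints Section 10.3.3.3 says: "Continuous variables and the change from baseline for these variables will be analyzed either by the MMRM or ANCOVA models described in Section 10.3.1". It leaves details to the SAP. Section 10.3.4, on safety variables, allows MMRM or ANCOVA and does not refer back to Section 10.3.1.

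**SAP.** Section 6.12.6 gives the treatment-period model for blood pressure, pulse, weight and BMI as an MMRM with treatment, baseline value, visit and "visit by treatment interaction as fixed factors and patient as the random factor". Lead-in weight gets the same form: "visit and treatment-by-visit interaction as fixed factors, and patient as the random factor". Neither sentence names a residual covariance, a fallback order or any stratification factor. Section 6.10 uses similar wording for lead-in insulin doses ("treatment-by-visit interaction in the model as fixed factors and patient as a random factor"), but lists all the strata. Section 6.12.7.1 uses it for antibody binding. By contrast, Section 6.11.1 states unstructured covariance for HbA1c, and Section 6.11.5 extends a similar model to the secondary variables.

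Section 6.11.6 contains no weight model, so Section 6.12.6 is the only place where the treatment-period repeated-measures model for the weight objective is written down.

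**The concern.** A mixed model with a single random patient effect and no stated residual structure normally means a random intercept with independent errors of equal variance. This is compound symmetry: the same variance at Week 2 as at Week 26, and the same correlation between any two visits. In the protocol that structure is the last resort after non-convergence.

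The assumption matters because the weight objective concerns one visit, the last. A model with one common variance gives Week 26 the average variance over all visits. If patients' weights drift apart as follow-up lengthens, that average is below the Week 26 variance and the interval is too short. Such growth is plausible: the model adjusts for baseline, Week 2 lies close to baseline, and prandial doses are titrated for 12 weeks. The documents do not show it, however.

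The second issue is traceability. Protocol Section 10.3.1 and SAP Section 6.1 say that changes of method and their justification will be described in the SAP or the clinical study report. The SAP gives none here, and its revision history does not mention this model. As the text stands, two programmers could fit different models and report different Week 26 intervals.

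**Working it through.** **The plan's own figure.** The documents give no SD, interval width or power for weight. The only design figure is HbA1c power (SAP Section 5.2), which supplies the arm sizes.

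- SE = 1.1 × √(1/320 + 1/160) = 0.1065
- 0.4/0.1065 − 1.96 = 1.796, and Φ(1.796) = 96.4% (stated: 96%)
- 480/0.85 = 564.7 (stated: 564)

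Both figures reproduce. Neither depends on the weight model.

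**Inputs.** The Schedule of Activities has seven weight visits after randomization: Weeks 2, 4, 8, 12, 18, 22 and 26. Tests are two-sided at 0.05 (SAP Section 6.1). Assumed: the SD of baseline-adjusted weight change moves linearly in time, by a factor R from Week 2 to Week 26.

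**Formula.** With complete data the random-intercept model gives every visit the mean of the seven visit variances. Hence

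- r = model SE / true SE at Week 26 = √(mean visit variance / Week 26 variance)
- actual coverage = 2Φ(1.96 r) − 1

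**One case in full, R = 2.** The relative SDs are 1, 1.083, 1.25, 1.417, 1.667, 1.833 and 2. The variances are 1, 1.174, 1.563, 2.007, 2.778, 3.361 and 4, with mean 2.269. So r = √(2.269/4) = 0.753, and coverage = 2Φ(1.476) − 1 = 86.0%.

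| SD at Week 26 relative to Week 2 | r | Coverage of nominal 95% interval |
|---|---|---|
| falls by one third | 1.28 | 98.8% |
| constant | 1.00 | 95.0% |
| ×1.25 | 0.90 | 92.1% |
| ×1.5 | 0.83 | 89.6% |
| ×2 | 0.75 | 86.0% |
| ×3 | 0.69 | 82.0% |

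**In kilograms.** An assumed rise in SD from 2.5 to 3.5 kg gives r = 0.853 and a type I error of 9.5%. A rise from 1.5 to 3.5 kg gives r = 0.723 and 16%. With an assumed Week 26 SD of 3 kg and 320 against 160 patients, the correct half-width is 1.96 × 3 × √(1/320 + 1/160) = 0.57 kg. The random-intercept half-width at R = 2 is 0.57 × 0.753 = 0.43 kg.

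**Check with dropout.** A random-intercept model was fitted by REML to simulated trials: 376 against 188 patients, seven visits, 15% random dropout, assumed serial correlation 0.9 per four weeks, 3000 runs per case. Coverage was 94.4% (constant SD), 89.3% (×1.5), 84.1% (×2) and 79.6% (×3). The formula is therefore close, and slightly optimistic once patients drop out.

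**Cost of the alternative.** An unstructured matrix for seven visits has 7 × 8 / 2 = 28 parameters.

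**The case against.** **The text never says compound symmetry.** It calls the model an MMRM, and SAP Section 6.3 describes MMRM as working through a variance-covariance structure. The phrase about patient may only identify the repeated-measures subject, in which case an unstructured residual is possible. This stands: compound symmetry is the literal reading, not a stated choice. It does not remove the point, because the structure is then unspecified.

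**The protocol does not bind every variable in Section 6.12.6.** Protocol Section 10.3.4 covers vital signs and weight as safety measures without pointing to Section 10.3.1, and the SAP may alter non-principal methods without an amendment. This stands for blood pressure and pulse. For weight as a tertiary objective, Section 10.3.3.3 does point to Section 10.3.1. Leaving details to the SAP does not explain why the SAP differs.

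**The strata follow a stated rule.** SAP Section 6.2 includes them in safety analyses as noted in Sections 6.11 and 6.12, and Section 6.12.6 notes none. That shows consistency within the SAP, but gives no reason for departing from the protocol. No harm from the omission has been quantified.

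**Every SD is assumed, and the error can reverse.** This is correct, and nothing in the documents bears on how the variance of weight, blood pressure or pulse moves over time.

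**Another analysis is planned.** A last-observation ANCOVA of weight does not pool variance across visits. That reduces the consequence. It does not make the MMRM interval valid, and it omits the strata too.

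**Conclusion.** The point holds as a specification gap with a conditional consequence. Section 6.12.6 should name its covariance structure. Its literal reading is a random-intercept model, which for the weight objective departs from the protocol's unstructured, stratified MMRM without a stated reason.

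The size depends on assumptions. Under the literal reading, SD growth of ×1.25 to ×2 takes actual coverage to about 92% to 86%. Constant SD causes no material error, and a falling SD makes the interval too wide.

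A reader might infer three stronger things, none of which the documents support:

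- That the SAP definitely fits compound symmetry, so the Week 26 interval is too narrow. The residual structure is unstated and no weight SDs are given.
- That the vital-sign models contradict the protocol in the same way. Section 10.3.4 does not tie them to Section 10.3.1.
- That a main conclusion is at risk. HbA1c has unstructured covariance stated, and weight is exploratory and outside multiplicity control (SAP Section 6.5).

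The finding is modest, but worth correcting because the remedy is short and the intended model already exists.

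**What to change.** In SAP Section 6.12.6, replace the random-patient phrase, for both the treatment and lead-in periods, with an unstructured within-patient covariance, the fallback order of Section 6.11.1 and Kenward-Roger degrees of freedom. Add the randomization strata, including the HbA1c stratum, to the weight model.

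Use the same covariance wording in two other places:

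- **Section 6.10.** The strata are already listed, so only the covariance wording changes. This model compares groups before randomized treatment and serves as a comparability check.
- **Section 6.12.7.1.** As written, the model covers only patients with a positive treatment-emergent antibody response. Their number is unknown, so the unstructured fit may not converge and the fallback order matters.

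The cost is a few sentences in the SAP. The covariance specification is already defined for HbA1c and can be reused. The downside is more covariance parameters: 28 for the seven weight visits, well supported by 564 randomized patients. That reassurance does not extend to the antibody model.

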**Baseline and Post-Baseline Definitions and Patient Population by Study Period and Type of Analysis**

Study Period/Analysis	Patient Population	Baseline Observations	Post-Baseline Observations
1,5-AG	All Randomized Patients with a baseline and at least one post-baseline observation	Visit 8 prior to initiation of IP	Visits 11, 15, and 18 prior to discontinuation of IP AND Last of Visits 9-18 prior to discontinuation of IP

Health outcomes: ITSQ, EQ-5D-5L, EQ- VAS, WPAI-GH	All Randomized Patients with a baseline and a post- baseline observation	Last of Visits 1-8	Last of Visits 9-18 prior to discontinuation of IP
Safety Laboratory Tests (chemistry, hematology, lipids) – continuous analysis	All Patients in the Safety Population with a baseline and a post-baseline observation	Last of Visit 1-8	Visit 18 (planned) AND last of Visits 9-18 (planned including early discontinuation visits) regardless of IP use
Safety Laboratory Tests (chemistry, hematology, lipids) – categorical analysis	All Patients in the Safety Population with a normal baseline (with respect to the direction being analyzed) and a post- baseline observation	Visits 1-8 (including unplanned tests)	Visits 9-18 (including unplanned tests) regardless of IP use
TEAEs	All Patients in the Safety Population	Prior to first dose of randomized IP (or Visit 8 date if the dose date is missing) but after the first dose of open-label insulin lispro in the Lead-in Period	From first dose of randomized IP to last dose of randomized IP AND From first dose of randomized IP to Visit 801
Hypoglycemia events	Safety Population	All Visits 2-8	All Visits 9-18 prior to discontinuation of IP
Weight and vital signs	All Patients in the Safety Population with a baseline and a post-baseline observation	Last of Visits 2-8	Visits 9-18 prior to discontinuation of IP AND Visits 9-801 regardless of IP use
Anti-insulin lispro antibodies	Safety Population	Visit 2	Visits 3-801 regardless of IP use

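### The treatment-emergent vital-sign percentages keep patients already outside the limit at baseline in the denominator, although they cannot become cases, unlike the laboratory rule

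*SAP*

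**What the plan says.** SAP 6.12.6 states the denominator for the categorical vital-sign and weight analysis: the percentages "will be summarized by treatment group for patients who have both baseline and at least 1 postbaseline measurement". It then defines the cases. For high values: "A treatment-emergent high result is defined as a change from a value less than or equal to the high limit at all baseline visits". For low values: "A treatment-emergent low result is defined as a change from a value greater than or equal to the low limit at all baseline visits". In both directions a postbaseline value must also cross the limit and meet the change threshold in Table 6.6. The arms are compared by Fisher's exact test.

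The Weight and vital signs row of Table 6.2 gives the population as "All Patients in the Safety Population with a baseline and a post-baseline observation". It sets baseline as the last value from Visits 2 to 8.

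The laboratory analysis in SAP 6.12.5 opens with almost the same denominator phrase and the same case definitions, then adds: "Only patients who have normal baseline values for the analysis being performed will be included in the analysis for treatment-emergence". Table 6.2 repeats this in a separate row for categorical laboratory tests, limited to patients "with a normal baseline (with respect to the direction being analyzed").

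**The concern.** A patient with one baseline systolic reading above the high limit cannot meet the high-case definition, which requires "a change from a value less than or equal to the high limit at all baseline visits". The stated denominator still includes that patient. The numerator is drawn from patients at risk and the denominator from everyone with data.

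Vital signs are a named endpoint of the tertiary safety objective, and these percentages are tested between arms. Three things are at stake: the absolute incidence in each arm, the absolute difference between arms, and comparability with the laboratory tables, which use the same treatment-emergent label on an at-risk basis. Two programmers could also produce different tables, one following 6.12.6 literally and the other carrying over the 6.12.5 rule.

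**Working it through.** The plan states no figure for treatment-emergent vital signs, so there is none to reproduce.

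**Inputs from the documents**
- Case and denominator rules: SAP 6.12.6. Comparison rule: SAP 6.12.5 and Table 6.2.
- High systolic limit 140 with a rise of at least 20; high diastolic limit 90 with a rise of at least 10; low systolic limit 90 with a fall of at least 20 (SAP Table 6.6). The text requires a value beyond the limit while Table 6.6 includes 140 and 90 themselves; the point holds under either reading.
- Vital-sign readings in Protocol Section 2: Visits 2, 5, 7 and 8 before treatment, and seven visits from Visit 10 to Visit 18 on treatment.
- 564 randomized 2:1, so 376 and 188 (SAP 5.2).
- No numeric blood pressure limit for entry (Protocol 6.1 and 6.2). Criterion 12 leaves vital signs to the investigator's judgment.

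**Step 1: algebra.** Let q be the share of evaluable patients outside the limit at baseline and r the incidence among the rest.
- Reported percentage = r × (1 − q).
- With equal q in both arms, reported risk difference = (1 − q) × (r_T − r_C).
- Risk ratio = r_T(1 − q) / [r_C(1 − q)] = r_T / r_C, unchanged.

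For an assumed r of 15%, the table would show 13.5%, 12%, 10.5%, 9% and 7.5% at q = 10%, 20%, 30%, 40% and 50%.

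**Step 2: plausible q.** All blood pressure values here are assumptions. Systolic pressure is taken as normal with mean 130, between-patient SD 11 and visit-to-visit SD 8, and the rise is measured from the last baseline reading.
- Single last reading: q = P(Z > 10/√(11² + 8²)) = P(Z > 0.735) = 23%. Simulated incidence at risk is 13.1%; reported 13.1% × 0.77 = 10.1%.
- Four readings, all required to be within the limit: simulated q = 44%. Incidence at risk is 8.4%; reported 8.4% × 0.56 = 4.7%.
- Over means 125 to 135, between-patient SDs 11 to 14 and visit SDs 8 to 10, q runs from 29% to 66% with four readings and from about 13% to 39% with one.
- High diastolic (mean 78, SDs 7 and 6, four readings): q = 24%, about 9% reported against about 12% at risk.
- Low systolic: q is about 1% or less, so there is almost no effect. Low diastolic: about 7% with four readings.

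**Step 3: effect on the comparison.** Take q = 30% in both arms and at-risk incidences of about 20% and 12%.

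| Basis | LY900014 | Insulin lispro | Difference | Ratio | Fisher p |
|---|---|---|---|---|---|
| At risk | 53/263 = 20.2% | 16/132 = 12.1% | 8.0 points | 1.66 | 0.050 |
| As planned | 53/376 = 14.1% | 16/188 = 8.5% | 5.6 points | 1.66 | 0.058 |

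At q = 20% the corresponding p-values are 0.047 and 0.039, so the small shift in p has no fixed direction.

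**Step 4: chance imbalance in q.** With q = 0.44, the SD of the difference in q between arms is √[0.44 × 0.56 × (1/376 + 1/188)] = 4.4 points. That is the SD of the not-at-risk share. Its effect on the reported percentages is r times this: 0.084 × 4.4 = 0.4 points. The ordinary sampling SE of the reported difference is √[0.047 × 0.953 × (1/376 + 1/188)] = 1.9 points. Over five scenarios in the assumed range, the effect was 0.25 to 0.76 points against SEs of 1.7 to 2.5.

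**The case against.** The percentage of all evaluable treated patients with a treatment-emergent value is a legitimate summary if labelled as such. The SAP does something similar for adverse events, where a patient already at maximum baseline severity for a term stays in the denominator. The opening phrase may also be only a data-availability condition, since 6.12.5 uses nearly the same words before adding its restriction; the omission in 6.12.6 may be a drafting gap. Finally, blood pressure and pulse are also analyzed as continuous variables by MMRM and ANCOVA with baseline in the model, so a shift would be visible anyway.

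Much of this stands, and it limits the importance of the point. It does not remove it. The SAP chose the at-risk basis for laboratory tests, stated it twice, and left vital signs without it under the same label. If the omission is a drafting gap, the remedy is the same sentence.

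Two stronger readings are tempting and should be set aside:
- A reader might infer that a chance imbalance in baseline hypertension could create a spurious difference between arms of about 4 points. That figure is the SD of the not-at-risk share; the effect on the percentages is well under 1 point and small beside sampling error.
- A reader might infer that a hypotensive effect of the treprostinil excipient could be hidden. The signal there would be low pressure, and for low systolic pressure q is negligible. Protocol 3.3 also describes treprostinil as unmeasurable in serum at doses expected in clinical use.

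**Conclusion.** The mismatch between numerator and denominator is in the current text, and Table 6.2 confirms it. Followed literally, the plan reports the at-risk incidence times (1 − q), so both the percentages and the absolute difference are diluted whenever any patient is outside the limit at baseline.

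The size cannot be computed from the documents. It depends on assumed blood pressure values and on which baseline is meant: the case definition uses all baseline visits, while Table 6.2 uses the last of Visits 2 to 8. In the systolic example that choice alone moves q from about 44% to about 23%. Neither figure is a prediction for this trial, and criterion 12 makes the upper end of the range less certain.

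The effect matters mainly for high blood pressure. A reader might infer that the safety comparison is biased; the documents do not support that. Randomization balances q on average, the risk ratio is unchanged in expectation, and Fisher's test moves little. Safety is a tertiary objective without multiplicity control, and no primary or multiplicity-adjusted conclusion is touched. The textual mismatch is clear; the priority is minor.

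**What to change.** In SAP 6.12.6, add for the categorical blood pressure and pulse analyses only: *Only patients whose values are within the limit for the direction being analyzed at all baseline visits, and who have at least 1 postbaseline measurement, will be included.*

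In Table 6.2, give categorical blood pressure and pulse their own row with this population, as categorical laboratory tests already have. Set its baseline entry to all baseline visits for the limit condition, and state which value is the reference for the change thresholds in Table 6.6. Weight keeps all patients with a baseline and a postbaseline value, because Table 6.6 gives it a 7% change and no absolute limit.

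The cost is one sentence, one table row and one program filter. The downside is smaller denominators that differ by parameter and direction, as the laboratory tables already have; each should be printed beside its percentage.
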